EPQ5: Compared to your patient's previous experience with treatment X, how would you rate the impact on patient's daily activities (such as shopping, bathing, social engagements, scheduling vacations, activities at work, attendance at work, etc.) due to skin reactions associated with tirbanibulin (Klisyri®) use in the original AK treated area?		Mean (SD), Median,Min,Max
1. Much better with tirbanibulin	n (%)	
2. Somewhat better with tirbanibulin	n (%)	

3. Same with tirbanibulin	n (%)
4. Somewhat worse with tirbanibulin	n (%)
5. Much worse with tirbanibulin	n (%)
 (1 / 2) Much / somewhat better with tirbanibulin	n (%)
(3) Same with tirbanibulin	n (%)
(4 / 5) Somewhat / much worse with tirbanibulin	n (%)

EPQ6: Compared to your patient's previous experience with topical treatment X for AK, how would you rate the convenience / ease of use (such as frequency of use, easy to follow instructions, comfortable at apply, etc.) associated with tirbanibulin (Klisyri®) treatment?

1. Ease of use & convenience was much better with tirbanibulin	n (%)
2. Ease of use & convenience was somewhat better with tirbanibulin	n (%)
3. Ease of use & convenience was the same with tirbanibulin	n (%)
4. Ease of use & convenience was somewhat worse with tirbanibulin	n (%)
5. Ease of use & convenience was much worse with tirbanibulin	n (%)
 (1 / 2) Ease of use & convenience was much / somewhat better with tirbanibulin	n (%)
(3) Ease of use & convenience was the same with tirbanibulin	n (%)
(4 / 5) Ease of use & convenience was somewhat / much worse with tirbanibulin	n (%)

EPQ7: Compared to your patient's previous experience with topical treatment X for AK, how would you rate your overall satisfaction (considering the factors such as convenience/ ease of use, duration and severity of skin reactions, impact on patient's daily life, etc.) with tirbanibulin (Klisyri®) treatment?

1. My satisfaction is much better with tirbanibulin	n (%)
2. My satisfaction is somewhat better with tirbanibulin	n (%)
3. My satisfaction is same with tirbanibulin	n (%)
4. My satisfaction is somewhat worse with tirbanibulin	n (%)
5. My satisfaction is much worse with tirbanibulin	n (%)
 (1 / 2) My satisfaction is much / somewhat better with tirbanibulin	n (%)
(3) My satisfaction is same with tirbanibulin	n (%)
(4 / 5) My satisfaction is somewhat / much worse with tirbanibulin	n (%)

Note: *EPQ3 – EPQ7 only asked if patient was indicated using a topical treatment for AK prior to the start of the study. Treatment X refers to this topical treatment(s) and was piped in from the baseline clinician survey.

Table 2.21 Subgroup Analysis of Clinician's Relative Satisfaction of Tirbanibulin, Regarding Duration of Skin Reactions

% Much / Somewhat Better	Week 8 n (%)	Week 24 n (%)
Subgroups		
Gender		
Male		
Female		
p -value		
Age Group		
≤ 49 years		
50 – 64 Years		
≥ 65 years		
p -value		
AK Treatment Location		
Face		
Scalp		
Both		
p -value		
Fitzpatrick Skin Type		
I / II		
III / IV / V / VI		
p -value		
Skin Photodamage		
Absent/mild		
Moderate/Severe		
p -value		
History of Skin Cancer		
Yes		
No		
p -value		
Prior Treatment Experience: Use of Cryosurgery		
Yes		
No		
p -value		
Prior Treatment Experience: Use of Other Topical Treatments		
Yes		
No		

p -value		
Prior Treatment Experience: Treatment Naïve at Baseline		
Yes		
No		

P-values correspond to difference between strata within respective time periods.

Table 2.22 Subgroup Analysis of Clinician's Relative Satisfaction of Tirbanibulin, Regarding Severity of Skin Reactions

% Much / Somewhat Better	Week 8 n (%)	Week 24 n (%)
Subgroups		
Gender		
Male		
Female		
p -value		
Age Group		
≤ 49 years		
50 – 64 Years		
≥ 65 years		
p -value		
AK Treatment Location		
Face		
Scalp		
Both		
p -value		
Fitzpatrick Skin Type		
I / II		
III / IV / V / VI		
p -value		
Skin Photodamage		
Absent/mild		
Moderate/Severe		
p -value		
History of Skin Cancer		
Yes		
No		
p -value		
Prior Treatment Experience: Use of Cryosurgery		
Yes		
No		
p -value		
Prior Treatment Experience: Use of Other Topical Treatments		
Yes		
No		

p -value		
Prior Treatment Experience: Treatment Naïve at Baseline		
Yes		
No		

P-values correspond to difference between strata within respective time periods.

Table 2.23 Subgroup Analysis of Clinician's Relative Satisfaction of Tirbanibulin, Regarding its Impact on Daily Activities

% Much / Somewhat Better	Week 8 n (%)	Week 24 n (%)
Subgroups		
Gender		
Male		
Female		
p -value		
Age Group		
≤ 49 years		
50 – 64 Years		
≥ 65 years		
p -value		
AK Treatment Location		
Face		
Scalp		
Both		
p -value		
Fitzpatrick Skin Type		
I / II		
III / IV / V / VI		
p -value		
Skin Photodamage		
Absent/mild		
Moderate/Severe		
p -value		
History of Skin Cancer		
Yes		
No		
p -value		
Prior Treatment Experience: Use of Cryosurgery		
Yes		
No		
p -value		
Prior Treatment Experience: Use of Other Topical Treatments		
Yes		
No		

p -value		
Prior Treatment Experience: Treatment Naïve at Baseline		
Yes		
No		
p -value		

P-values correspond to difference between strata within respective time periods.

Table 2.24 Subgroup Analysis of Clinician's Relative Satisfaction of Tirbanibulin, Regarding its Convenience / Ease of Use

% Much / Somewhat Better	Week 8 n (%)	Week 24 n (%)
Subgroups		
Gender		
Male		
Female		
p -value		
Age Group		
≤ 49 years		
50 – 64 Years		
≥ 65 years		
p -value		
AK Treatment Location		
Face		
Scalp		
Both		
p -value		
Fitzpatrick Skin Type		
I / II		
III / IV / V / VI		
p -value		
Skin Photodamage		
Absent/mild		
Moderate/Severe		
p -value		
History of Skin Cancer		
Yes		
No		
p -value		
Prior Treatment Experience: Use of Cryosurgery		
Yes		
No		
p -value		
Prior Treatment Experience: Use of Other Topical Treatments		
Yes		
No		

p -value		
Prior Treatment Experience: Treatment Naïve at Baseline		
Yes		
No		

P-values correspond to difference between strata within respective time periods.

Table 2.25 Subgroup Analysis of Clinician's Overall Satisfaction with Tirbanibulin Relative to Previous Topical Treatments

% Much / Somewhat Better	Week 8 n (%)	Week 24 n (%)
Subgroups		
Gender		
Male		
Female		
p -value		
Age Group		
≤ 49 years		
50 – 64 Years		
≥ 65 years		
p -value		
AK Treatment Location		
Face		
Scalp		
Both		
p -value		
Fitzpatrick Skin Type		
I / II		
III / IV / V / VI		
p -value		
Skin Photodamage		
Absent/mild		
Moderate/Severe		
p -value		
History of Skin Cancer		
Yes		
No		
p -value		
Prior Treatment Experience: Use of Cryosurgery		
Yes		
No		
p -value		
Prior Treatment Experience: Use of Other Topical Treatments		
Yes		
No		

p -value		
Prior Treatment Experience: Treatment Naïve at Baseline		
Yes		
No		

P-values correspond to difference between strata within respective time periods.

Table 2.26 Factors Influencing Overall Clinician Satisfaction with Tirbanibulin in the Original Treated Area

EPQ8 What factors influenced your response to the previous question about your overall satisfaction with tirbanibulin (Klisyri®)? **Selected**

Domain	Week 8 N=x	Week 24 N=x
[EPQ8r1]. Product convenience: Length of treatment, frequency, and easiness to take, etc.	n (%)	n (%)
[EPQ8r2] Product effectiveness: Impact on skin appearance.	n (%)	n (%)
[EPQ8r3] Product effectiveness: Impact on AK lesion clearance.	n (%)	n (%)
[EPQ8r4] Product effectiveness: Amount of time it takes to start working.	n (%)	n (%)
[EPQ8r5] Product side-effects: Amount of time it takes for local skin reactions to resolve.	n (%)	n (%)
[EPQ8r6] Product side-effects: Number and type of local skin reactions.	n (%)	n (%)
[EPQ8r7] Product side-effects: Severity of the local skin reactions.	n (%)	n (%)
[EPQ8r8] Product tolerability: Ability to adhere to treatment dose, or intensity.	n (%)	n (%)
[EPQ8r9] Other: EPQ8r9oe	n (%)	n (%)

Table 2.27 Top-3 Factors Influencing Overall Clinician Satisfaction with Tirbanibulin in the Original Treated Area at Week 8

EPQ8A Among the list of factors that influenced your overall satisfaction with tirbanibulin (Klisyri®), please identify the three most important factors and rank them on a scale of importance from 1 to 3, where 1 is the first most important factor, 2 is the second most important factor and 3 is the third most important factor to you, by entering a number in the boxes next to only those factors in the following list.

Domain	Rank 1	Rank 2	Rank 3	Average Rank
[EPQ8Ar1] Product convenience: Length of treatment, frequency, and easiness to take, etc. (N=x)	n (%)	n (%)	n (%)	
[EPQ8Ar2] Product effectiveness: Impact on skin appearance. (N=x)	n (%)	n (%)	n (%)	
[EPQ8Ar3] Product effectiveness: Impact on AK lesion clearance. (N=x)	n (%)	n (%)	n (%)	
[EPQ8Ar4] Product effectiveness: Amount of time it takes to start working. (N=x)	n (%)	n (%)	n (%)	
[EPQ8Ar5] Product side-effects: Amount of time it takes for local skin reactions to resolve. (N=x)	n (%)	n (%)	n (%)	
[EPQ8Ar6] Product side-effects: Number and type of local skin reactions. (N=x)	n (%)	n (%)	n (%)	
[EPQ8Ar7] Product side-effects: Severity of the local skin reactions. (N=x)	n (%)	n (%)	n (%)	
[EPQ8Ar8] Product tolerability: Ability to adhere to treatment dose, or intensity. (N=x)	n (%)	n (%)	n (%)	
[EPQ8Ar9] Other: (N=x) EPQ8Ar9oe	n (%)	n (%)	n (%)	

Note: Data pulled from patient DCF

Table 2.28 Top-3 Factors Influencing Overall Clinician Satisfaction with Tirbanibulin in the Original Treated Area at Week 24

EPQ8A Among the list of factors that influenced your overall satisfaction with tirbanibulin (Klisyri®), please identify the three most important factors and rank them on a scale of importance from 1 to 3, where 1 is the first most important factor, 2 is the second most important factor and 3 is the third most important factor to you, by entering a number in the boxes next to only those factors in the following list.

Domain	Rank 1	Rank 2	Rank 3	Average Rank
[EPQ8Ar1] Product convenience: Length of treatment, frequency, and easiness to take, etc. (N=x)	n (%)	n (%)	n (%)	
[EPQ8Ar2] Product effectiveness: Impact on skin appearance. (N=x)	n (%)	n (%)	n (%)	
[EPQ8Ar3] Product effectiveness: Impact on AK lesion clearance. (N=x)	n (%)	n (%)	n (%)	
[EPQ8Ar4] Product effectiveness: Amount of time it takes to start working. (N=x)	n (%)	n (%)	n (%)	
[EPQ8Ar5] Product side-effects: Amount of time it takes for local skin reactions to resolve. (N=x)	n (%)	n (%)	n (%)	
[EPQ8Ar6] Product side-effects: Number and type of local skin reactions. (N=x)	n (%)	n (%)	n (%)	
[EPQ8Ar7] Product side-effects: Severity of the local skin reactions. (N=x)	n (%)	n (%)	n (%)	
[EPQ8Ar8] Product tolerability: Ability to adhere to treatment dose, or intensity. (N=x)	n (%)	n (%)	n (%)	
[EPQ8Ar9] Other: (N=x) EPQ8Ar9oe	n (%)	n (%)	n (%)	

Table 2.29 Unscheduled Patient Encounters Reported at Week 8

Domain	Week 8 (N=x)
[US1_1r1] Number of unscheduled in-person clinic visits:	n (%)
[US1_1r2] Number of unscheduled tele-health visits:	n (%)
[US1_1r3] Number of unscheduled phone calls:	n (%)

Table 2.30 Prior AK Treatment (To-Date) Including within the Past 6 Months

Character TH2 and TH3 (Start date prior to Klisyri®; End date within the past 6 months or No end date)	Baseline (N=x)
TH2A checked AND TH3=No Has not use any AK medication	n (%)
Topical medication	
[TH2r1] 5-Fluorouracil (5-FU)	
[TH2r2] Salicylic acid	
[TH2r3] Imiquimod	
[TH2r4] Ingenol mebutate	n (%)
[TH2r5] Diclofenac	
[TH2r6] Other [TH2r6oe]	
A	
B	
C	
Oral medication:	
[TH2r7] Isotretinoin	
Other	
A	n (%)
B	
C	
Other therapies:	
[TH2r8] Photodynamic therapy	
[TH2r9] Cryosurgery/Cryotherapy	
[TH2r10] Chemical/acid peel	
[TH2r11] Curettage	
[TH2r12] Laser therapy	n (%)
Other:	
A	
B	
C	

Note: Data from Clinician DCF; X patients had missing data; The denominator for the percentages is the number of patients with available data (N=X)

Table 2.31 AK Concomitant Medication Use During the 8-Week Observation Period

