12.3.3 Subgroup Analysis

Primary, secondary, and additional (non-safety) endpoints may be summarized and repeated for the following subgroups, if sample size permits, using FAS:

- AK Treatment location: face, scalp.
- Age groups: <49 years, 50-64 years, and ≥ 65 years.
- Fitzpatrick I/II, and III/IV/V/VI.
- Prior treatment experience, as applicable:
 - Cryosurgery vs. all others;
 - Other topical treatments vs. all others;
 - Treatment naïve vs. all others.
- Patients re-treated between Week-8 and Week-24 visits, vs. all others, as applicable.

Descriptive analyses of Safety data will be carried out using safety population dataset.

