5.3 Treatment Effectiveness Assessments

The effectiveness of tirbanibulin treatment will be assessed from the perspective of Site Investigators as well as the Subjects. It is expected that the Site Investigator assessments will be conducted via in-person visits/encounters at baseline, Week 8 and Week 24, and when in-person assessments are not feasible (owing to COVID-related travel restrictions), the assessments

maybe done via virtual/remote visits. The same evaluator at study site shall perform all evaluations for a subject during the study, as feasible.

5.3.1 *Investigator Global Assessment (IGA):*

Site Investigators to assess the status of subject's AK in the treated area on the face or scalp using the following IGA scale, at Weeks 8 and 24. The IGA should be representative of the investigator's overall general assessment of the subject's AK and take into account the quality, as well as the quantity, of AK lesions.

Outcome Measure	Score
Completely cleared - Approximately 100% clearance of AK lesions in the treated area	0
Partially cleared - Approximately $\geq 75\%$ clearance of AK lesions in the treated area	1
Moderately cleared - Approximately 50-74% clearance of AK lesions in the treated area	2
Minimally Cleared - Approximately <50% clearance of AK lesions in the treated area	3
Not Cleared - Approximately 0% clearance, i.e., all AK lesions remained in the treated area	4

5.3.2 *Severity of Skin Photodamage*

Site Investigators will be asked to rate the severity of skin photodamage in the AK treated area (at baseline, Weeks 8 and 24), on the following 4-point Likert scale:

Outcome Measure	Score
Absent - Smooth evenly pigmented skin	0
Mild - Freckling and/or other dyspigmentation	1
Moderate - Above plus mildly rough "dry" skin, fine wrinkling and/or telangiectasias or blotchy erythema	2

Severe - Above plus pronounced “dryness” and/or dyspigmentation and/or telangiectasia or erythema, and/or wrinkling, with or without areas of actinic purpura	3
---	---

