6.3.3 Subgroup Analysis

Primary, secondary, and additional (non-safety) endpoints may be summarized and repeated for the following subgroups, if sample size permits, using FAS:

- Gender: male and female
- Age groups: ≤ 49 years, 50-64 years, and ≥ 65 years.
- Fitzpatrick skin type: I/II, and III/IV/V/VI.
- Skin photodamage at baseline: absent/mild, moderate/severe.
- History of skin cancer: yes and no.
- AK Treatment location: face only, scalp only, both face & scalp.
- Prior treatment experience, as applicable:
 - Cryosurgery vs. all others;
 - Other topical treatments vs. all others;
 - Treatment naïve vs. all others.

Subgroup analyses based on patient retreatment status between Week-8 and Week-24 visits (Klisyri vs. other topicals vs. non topicals vs. not retreated) may be considered for relevant outcome measures, based on data availability.

Subgroup analyses will either assess the difference in outcomes within a specific strata at a given time period (for measures collected only at Week-8 and/or Week-24), or assess CFB within a specific strata (for measures collected at baseline and at Week-8 and/or week-24).

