6.6.3 Photodamage Severity Analyses

The proportion of Subjects with a severity of score of 0 (absent) and proportion of subjects with a severity score of 0 (absent) or 1 (mild) in clinician assessment of AK-related photodamage at baseline, and at Weeks 8 and 24 will be assessed respectively. CFB in photodamage severity score at Weeks 8 and 24 will be explored and reported using descriptive statistics. This analysis will be conducted using the FAS dataset.

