Subgroups	Symptoms			Emotions			Functioning		
	Baseline n, Mean	Wk-8 n, Mean	P	Baseline n, Mean	Wk-8 n, Mean	P	Baseline n, Mean	Wk-8 n, Mean	P
Gender									
Male									
Female									
Age Group									
≤ 49 years									
50 – 64 Years									
≥ 65 years									
AK Treatment Location									
Face									
Scalp									
Both									
BL Fitzpatrick Skin Type									
I / II									
III / IV / V / VI									
BL Skin Photodamage									
Absent/mild									
Moderate/Severe									
BL History of Skin Cancer									
Yes									
No									
Prior Treatment Experience: Use of Cryosurgery									
Yes									
No									
Prior Treatment Experience: Use of Other Topical Treatments									
Yes									
No									
Prior Treatment Experience: Treatment Naïve at Baseline									
Yes									
No									

P-values correspond to CFB at week-8, within respective strata.

Table 1.10 Patient Evaluation of Overall Appearance in the Original Treated Area

Questions	PER1 Week 8 (N=x)	PER24_1 Week 24 (N=x)
Compared to [8 or 24] weeks ago (at the beginning of the study), how has the overall appearance of the skin in the original AK treated area changed?	Mean (SD), Median, Min, Max	Mean (SD), Median, Min, Max
1. Much Worse	n (%)	n (%)
2. Somewhat Worse	n (%)	n (%)
3. No Change	n (%)	n (%)
4. Somewhat Improved	n (%)	n (%)
5. Much Improved	n (%)	n (%)
(1 / 2) Much / Somewhat Worse	n (%)	n (%)
(3) No Change	n (%)	n (%)
(4 / 5) Somewhat / Much Improved	n (%)	n (%)

Table 1.11 Subgroup Analysis of Patient Evaluation of Overall Appearance in the Original Treated Area

Subgroups	% Somewhat/Much Improved	Week 8 n (%)	Week 24 n (%)
Gender			
Male			
Female			
p -value			
Age Group			
≤ 49 years			
50 – 64 Years			
≥ 65 years			
p -value			
AK Treatment Location			
Face			
Scalp			
Both			
p -value			
Fitzpatrick Skin Type			
I / II			
III / IV / V / VI			
p -value			
Skin Photodamage			
Absent/mild			
Moderate/Severe			
p -value			
History of Skin Cancer			
Yes			
No			
p -value			
Prior Treatment Experience: Use of Cryosurgery			
Yes			
No			
p -value			
Prior Treatment Experience: Use of Other Topical Treatments			
Yes			
No			

p -value		
Prior Treatment Experience: Treatment Naïve at Baseline		
Yes		
No		

p-values correspond to difference between strata within respective time periods.

Table 1.12 Treatment Satisfaction Questionnaire for Medication (TSQM-9): Patient Scores in the Original Treated Area

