How do you rate the current severity of skin photodamage in the AK affected area?			
Responses will need to be recoded	AK4	AK8_3	AK8_3
0. Absent	n (%)	n (%)	n (%)
1. Mild	n (%)	n (%)	n (%)
2. Moderate	n (%)	n (%)	n (%)
3. Severe	n (%)	n (%)	n (%)
Absent/ Mild (0/1)	n (%)	n (%)	n (%)
Moderate/Severe (2/3)	n (%)	n (%)	n (%)
Who did the evaluation of patient's AK severity?			
1. Dermatologist	AK5	AK8_4	AK8_4
2. Nurse practitioner	n (%)	n (%)	n (%)
3. Physician's assistant	n (%)	n (%)	n (%)
How was the evaluation of AK severity done?			
1. During in-person patient visit (face-to-face)	AK6	AK8_5	AK8_5
2. Via tele-health visit (video)	n (%)	n (%)	n (%)

Table 2.8 CFB for Current Severity of Photodamage in the Original Treated Area

Domain	CFB in Proportion at Week 8 N=X (%)	p-value	CFB in Proportion at Week 24 N=X (%)	p-value
How do you rate the current severity of skin photodamage in the AK affected area?				
Absent (0)	%		%	
Mild / Moderate / Severe (1 / 2 / 3)	%	p	%	p
Absent / Mild (0 / 1)	%		%	
Moderate / Severe (2 / 3)	%	p	%	p

Table 2.9 Subgroup Analysis of Current Severity of Photodamage in the Original Treated Area

Subgroups	% Absent / Mild (0 / 1)		Baseline		Week 8		Week 24	
		n (%)		n (%)	P	n (%)	P	
Gender								
Male								
Female								
Age Group								
≤ 49 years								
50 – 64 Years								
≥ 65 years								
AK Treatment Location								
Face								
Scalp								
Both								
Fitzpatrick Skin Type								
I / II								
III / IV / V / VI								
Skin Photodamage								
Absent/mild								
Moderate/Severe								
History of Skin Cancer								
Yes								
No								
Prior Treatment Experience: Use of Cryosurgery								
Yes								
No								
Prior Treatment Experience: Use of Other Topical Treatments								
Yes								
No								
Prior Treatment Experience: Treatment Naïve at Baseline								
Yes								
No								

P-values correspond to CFB at respective time periods, within the corresponding strata.

Table 2.10 Clinician Evaluation of IGA in the Original Treated Area

Character	Week 8 (N=x)	Week 24 (N=X)
Overall, how is your patient's AK in the original treated area right now?		
Responses will need to be recoded	AK8_1	AK8_1
0. Completely Cleared	n (%)	n (%)
1. Partially Cleared	n (%)	n (%)
2. Moderately Cleared	n (%)	n (%)
3. Minimally Cleared	n (%)	n (%)
4. Not Cleared	n (%)	n (%)
(0 / 1) Completely/Partially Cleared	n (%)	n (%)
2 Moderately Cleared	n (%)	n (%)

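### SAP Table 2.9 tests change in photodamage within strata formed from the same baseline rating, so four of its p-values can be significant with no net change

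*SAP*

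**What the plan says.** SAP section 6.3.3 lists among its subgroup factors "Skin photodamage at baseline: absent/mild, moderate/severe". For outcomes that have a baseline value, the same section says the subgroup analysis will "assess CFB within a specific strata (for measures collected at baseline and at Week-8 and/or week-24".

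Table 2.9 (SAP section 7.2) applies this to photodamage. Its outcome is the percentage rated absent or mild (scores 0 or 1), with a p-value column at Week 8 and another at Week 24. Its footnote reads: "P-values correspond to CFB at respective time periods, within the corresponding strata". Two of its rows are absent/mild and moderate/severe skin photodamage. Table 2.9 does not mark this factor as a baseline factor, but section 6.3.3 does, and Table 1.9 labels the same factor "BL Skin Photodamage".

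Table 2.8 already gives the whole-cohort change in the same proportion, with p-values at both visits. The text in section 6.6.3 goes no further than description: "CFB in photodamage severity score at Weeks 8 and 24 will be explored and reported using descriptive statistics". Baseline photodamage is not in the protocol's subgroup list (section 12.3.3). Nothing in either document exempts these two rows of Table 2.9 or leaves their p-values blank.

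**The concern.** The stratum and the outcome are one variable: the same investigator rating, at the same visit, cut at the same point. Everyone in the absent/mild row starts as a success and everyone in the moderate/severe row starts as a failure. In the first row a patient can only stay or get worse; in the second, only stay or improve.

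A paired test of change compares switches in the two directions. Here one direction is impossible by construction, so the null hypothesis holds only if nobody's rating ever changes. The p-value then does no more than count the patients who switched. An imperfectly repeatable rating will produce apparent worsening in one row and apparent improvement in the other even when no patient's skin has changed.

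At stake is a misleading line in the output. A small p-value in the moderate/severe row could be quoted as a benefit of treatment on photodamage, when the mirror-image row and the whole-cohort test show no net change.

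**Working it through.** The plan states no test, significance level or sample-size calculation for this analysis, so there is no figure of its own to reproduce. I assume a two-sided 0.05 level and use McNemar's test as the natural choice for paired proportions, with variants.

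**Cells affected.** Table 2.9 has 20 stratum rows: gender 2, age 3, location 3, skin type 2, photodamage 2, skin cancer history 2, and three prior-treatment factors with 2 each. With two visits that is 20 × 2 = 40 p-value cells, of which 2 × 2 = 4 are affected.

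**How many switches give p < 0.05.** Let k be the number of patients in a row who switch. All k go the same way.

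| Test | Formula | Results | Switches needed |
|---|---|---|---|
| Exact McNemar | p = 2 × 0.5^k | k=5: 0.0625; k=6: 0.031; k=10: 0.002 | 6 |
| McNemar, continuity-corrected | χ² = (k−1)²/k | k=5: 0.074; k=6: 0.041 | 6 |
| McNemar, uncorrected | χ² = k | k=3: 0.083; k=4: 0.046 | 4 |
| Fisher, ignoring pairing (row size 50 to 250) | n/n against (n−k)/n | k=5: 0.056 to 0.061; k=6: 0.027 to 0.030 | 6 |

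**An example that needs no error rate.** Suppose 6 patients move from absent/mild to moderate/severe and 6 move the other way, which is 12 of 300, or 4%. Each row gives exact p = 0.031. The whole-cohort test compares 6 with 6 and gives p = 1.00. With 10 each way, the rows give p = 0.002 and the cohort again gives 1.00. The two rows thus report separately the two off-diagonal counts whose difference Table 2.8 tests.

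**How often with no true change.** Suppose each patient's true status is constant, and each rating is wrong with probability e, equal in both directions. A patient contributes a switch to a given row if exactly one of the two ratings is wrong in the relevant order. That probability is e(1−e) whether the patient is truly absent/mild or truly moderate/severe, so baseline prevalence drops out. If in a share r of patients the error is identical at both visits, those patients never switch. The count in each row is then Binomial(N, (1−r)e(1−e)). For example, at N = 300, e = 2% and r = 0, the expected count is 300 × 0.02 × 0.98 = 5.88.

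Probability of at least 6 switches, that is p < 0.05 in a given cell (N = 300):

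| Error e | r = 0 | r = 50% | r = 80% |
|---|---|---|---|
| 1% | 8% | 0.4% | about 0% |
| 2% | 54% | 7.7% | 0.1% |
| 3% | 87% | 27% | 0.9% |
| 5% | >99% | 72% | 6.9% |

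At N = 240 and e = 2%, the three columns give 33%, 3.2% and 0.04%.

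A simulation of the independent-error model (N = 300, true absent/mild share 20%, 30% or 50%, 1,000 runs per setting) gave p < 0.05 in each of the four cells in 52% to 55% of runs at 2% error and at least 98.8% at 5%. The whole-cohort test on the same data rejected in 1.7% to 4.6% of runs at errors of 2% to 10%, which is where a valid test should be.

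**What is unknown.** The documents give neither e nor r. They point both ways on persistence: "The same evaluator at study site shall perform all evaluations for a subject during the study, as feasible" favours repeatable ratings, while Table 2.7 allows the evaluation to be done in person or by video and by different types of clinician.

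**The case against.** The strongest objection is that any within-stratum p-value can be significant while the cohort is flat. If men improved and women worsened equally, both gender rows could be significant and both would be right. Disagreement with the cohort result is therefore not a fault in itself, and if the 6 switches in a row were real, the row would describe them correctly. That is fair. But gender is not defined by the outcome: with no true change and equal rating error, switches within men have no built-in direction and the test keeps its level. In the photodamage rows, rating error alone yields one-way switches, so real and spurious change look the same.

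Second, a p-value may never appear. Baseline is constant within each row, so one margin of the paired table is empty, and some software returns no McNemar result in that case. That is possible, since the SAP names no test. The cells would then be empty rather than misleading, but no more useful.

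Third, the rates above run from about 0% to over 99%, and with 80% persistence none exceeds 7%. They show the mechanism and do not give a firm size.

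Fourth, section 6.6.3 calls for description only, yet Table 2.8 also prints p-values and is left in place here. That is correct, and it means the descriptive wording is not the reason to remove these four. The reason is that they are degenerate.

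Finally, the reach is small. Both documents make subgroup summaries optional: "Primary, secondary, and additional (non-safety) endpoints may be summarized and repeated for the following subgroups, if sample size permits, using FAS" is the protocol's wording. The 100% and 0% baselines would be printed beside the p-values, where an attentive reader could see the artefact. All of this stands and limits the severity. None of it makes the four cells valid.

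**Conclusion.** The concern holds, as a minor point. That stratum and outcome coincide follows directly from SAP section 6.3.3 and the Table 2.9 shell, and needs no assumption beyond reading the row as baseline photodamage, which section 6.3.3 settles. The four p-values cannot serve as tests of change. Six one-way switches in a row are enough for p < 0.05 with exact or continuity-corrected McNemar or with Fisher, and four with uncorrected McNemar, assuming the conventional two-sided 0.05 level.

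The frequency of false significance is not established, because it rests on an unknown rating error and its persistence between visits. The whole-cohort test in Table 2.8, the other 36 p-value cells of Table 2.9, and the primary and secondary results do not have this defect.

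**What to change.** In Table 2.9, delete the Week 8 and Week 24 p-values in the two skin photodamage rows and label the factor as baseline, as Table 1.9 does. Keep the counts and percentages as description, or replace the two rows with a baseline-by-visit shift table. In either case add a footnote such as: *Baseline is 100% or 0% by definition of the stratum; change includes regression to the mean and rating error.* Read whole-cohort change in photodamage from Table 2.8.

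The cost is one edit to a table shell and one footnote before database lock. No analysis specified in the protocol is lost, because this stratum is not in the protocol's subgroup list and the whole-cohort comparison stays.
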